A limitation of existing research is that it tended to examine the effects of manipulating energy density for relatively low energy dense foods and foods are manipulated covertly during a single session, so consumers are not able to learn about the energy content(14). For example, in the two studies mentioned, the highest energy densities tested were 1.8kcal/g(16) and 2.2kcal/g(15) respectively. However, consumers often are exposed to and consume foods of higher energy density. In one UK fast food restaurant menu, main meal items ranged from 1.9kcal/g to 3.2 kcal/g(17). This may be an important consideration because recent observational research suggested that up to approximately 1.5-2kcal/g, individuals are relatively insensitive to changes in energy density, and there is no indication of compensation through altering meal size(18). However, upwards of approximately 1.5-2kcal/g, the authors proposed that individuals compensate for increases in energy density by selecting and consuming smaller meal sizes. The proposed explanation for this is that individuals rely on the volume of food as the dominant signal with energy dilute foods (i.e.<1.5) and rely on calorie content as the dominant signal for energy rich foods(18). The volume signal is related to gastric distention and the calorie content signal is related to both learned and unlearned effects. If correct, the proposed model has implications for food product energy reformulation, as it suggests that reducing the energy density of more energy dense food products (e.g. >2.5kcal/g to 2kcal/g) may not lead to reductions in energy intake because within this range of energy densities consumers adjust meal size to compensate for changes in energy density.

However, there has been no formal testing of the proposed model using experimental approaches and it is unclear how efficiently consumers learn about the density of energy dense foods and adjust their meal size accordingly. In a previous study, we tested whether consumers adjust the meal size when given foods varying in energy density. This previous study measured the meal size of three desserts that were familiar to participants with the same basic ingredients (vanilla yoghurt, vanilla ice cream, vanilla cheesecake) but varying in energy densities (1.2kcal/g, 1.9kcal/g, 3.5kcal/g), with the aim of understanding the extent to which learned energy density would influence intake.

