We aim to follow up on this previous study, by covertly manipulating the level of energy density of a meal, using the same parameters as the prior study. In this previous study the foods provided were noticeably different to participants, and so underlying preferences and differences in sensory and nutritional aspects of the meals may have influenced the amount consumed. Equally, this study did not measure whether later intake differed following consumption of desserts varying in energy density. For the present study, the foods provided will be variations on the same meal (loaded fries), so participant's expectations of the meals should be comparable. This will help us to understand whether reformulation to approximately 2kcal/g would lead to a reduction in energy intake, or if further reduction, below 1.5kcal/g is required to influence immediate eating behaviour positively by reducing energy intake. Additionally, if there are significant effects of energy density, it is vital to determine whether these changes are compensated for by consumers later on in the day.

Primary objectives: To observe differences in consumption (g/kcal) when participants are given a meal covertly manipulated to be low, medium or high in energy density.

Secondary objective: To measure later food intake, in order to observe any evidence of later compensation in response to experimental condition.

To measure intake over the full day, in order to understand whether one manipulated meal impacts daily energy intake.

Study Information

Hypotheses:

Based on Flynn et al(18), it is hypothesised that as the energy density of the lunch meal increases from low ED to medium ED, the amount of the lunch consumed (g) will remain similar, but due to the increased energy density, the calories consumed will increase.

As energy density of the lunch meal increases from medium ED to high ED, the amount of lunch consumed (g) will decrease, due to people compensating for the increase in energy density (i.e., participants will attend to satiety signals and adjust meal size).

Design Plan

Study type: Experiment - A researcher randomly assigns treatments to study subjects, this includes field or lab experiments. This is also known as an intervention experiment and includes randomized controlled trials.

Blinding: For studies that involve human subjects, they will not know the treatment group to which they have been assigned.

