Is there any additional blinding in this study? To attempt to reduce the likelihood of aim guessing, participants will be recruited to a study labelled as 'a study of diet on cognitive function'.

Study design: An experimental, within-subjects design. Participants will be asked to visit the lab for three consecutive weeks to complete some questionnaires and eat meals at lunch time and dinner time. Participants will complete all three conditions – low energy density, medium energy density and high energy density meals which will be eaten ad-libitum. Participants will be provided with a box of snacks to eat throughout the day if they wish to, and will return to the lab for dinner, where they will be served an ad-libitum meal and a dessert.

Randomization: Participants will complete all three conditions. The order the conditions are presented to participants will be randomised prior to arrival.

Sampling Plan

Existing Data: Registration prior to creation of data

Explanation of existing data: N/A

Data collection procedures: Participant database. If required, participants will also be recruited from the local community (e.g. adverts on social media/posters in the university)

Inclusion criteria:

- Currently reside in the UK
- Over the age of 18 years
- Fluent English speaker
- Like the test foods
- Have a BMI between the ranges of 18.5 and 35.

Exclusion criteria:

- Pregnant/breastfeeding
- Partaking in a fast or other restrictive eating for religious reasons at time of participation

- Currently following a diet
- On medication that affects appetite
- Being a smoker
- Current or historic eating disorder
- Dietary restrictions/intolerances including:
 - Any allergies
 - Vegan/vegetarian
 - Gluten-free
 - Dairy-free
 - Sugar-free

Procedure:

Once signed up, participants will attend a short screening session, where they will be asked to complete a medical history questionnaire, a baseline demographic questionnaire, have their height and weight measured, and check they like the test foods on offer.

Participants will be told upon registration that they should have the same breakfast the morning of each session. Arrangements will be made for the participants to arrive at the lab around the time they would usually eat their lunch (11.30-2.30) and be allocated to one of the following groups for each session (order randomised):

- Low energy density lunch
- Medium energy density lunch
- High energy density lunch

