At each lunch session, participants will be asked to report any foods or beverages (excluding water) consumed the morning of the study, to ensure nothing was consumed in the two hours prior to the study, and to ensure breakfast is similar across the three sessions. At each dinner session, participants will be asked to report any foods or beverages (excluding water) consumed that were not provided by the researchers.

Aim guessing (Appendix H)

At the end of their final visit, participants will be asked what they believe the aims of the study to be. Anyone that guesses the study aims to be investigating the influence of energy density on intake (e.g. the healthiness/energy content of meal on how much was consumed at lunch time or at dinner time) will be coded as being aware of study aims. One researcher will code awareness of aims and a second researcher will independently verify.

Participants will then be asked to rank the three lunch time meals in terms of level of energy density.

Additional tasks

Additional tasks will be completed to account for the study description of ‘A study of diet on cognitive function’. Before and after each lunch and dinner meal, participants will complete a Stroop task.

Study flow

	Visit 1	Visit 2	Visit 3
RECRUITMENT	Participants who could not take part in the previous mood, diet and sleep study will be contacted to take part in this study (Appendix A)		

SCREENING	
Participants will come into the lab to be screened. This will involve:
 
Medical history questionnaire
 
Baseline demographic questionnaire (Appendix B)
 
Height and weight measurement
 
Ensuring they like all test foods.
		
INFORMED CONSENT	
Participants will be asked to read the information sheet (Appendix C).
 
Participants who want to proceed will read the consent form and tick a box providing their consent (Appendix D).
		
RANDOMISATION	Before their first session, the order that meals are presented to participants will be randomized.		
BASELINE ASSESSMENTS (Inquisit)	Participants will complete a baseline demographic questionnaire, measures of hunger and fullness, and a cognitive task	Participants will complete measures of hunger and fullness and a cognitive task	Participants will complete measures of hunger and fullness and a cognitive task

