Participant characteristics will be presented in a table. Data will include age, gender, ethnicity, BMI, highest education level, perceived social status, childhood SEP, compensatory health beliefs and satiety awareness. Continuous variables will be summarised by means and standard deviations, categorical variables will be summarised by counts and percentages.

Primary analyses:

Two repeated-measures, within-subjects ANOVAs will assess lunchtime (manipulated meal) kcal and gram intake across the three conditions. Where significant main effects are identified, post-hoc pairwise comparisons will be performed to identify where these differences exist. Sensory ratings of the three meals will be compared using repeated-measures, within-subjects ANOVAs to assess whether all meals were rated equally. Results will be considered statistically significant at $p<0.05$.

Secondary analyses:

Two repeated-measures, within-subjects ANOVAs will assess later kcal and gram intake (dinner, dessert and snacks) across the three conditions (low ED, medium ED and high ED). Where significant main effects are identified, post-hoc analyses will be performed to identify where these differences exist.

A repeated-measures, within-subjects ANOVA will assess daily energy intake (sum of lunch, dinner, dessert, snacks and additional food) across the three conditions. Where significant main effects are identified, post-hoc analyses will be performed to identify where these differences exist.

To account for multiple comparisons, results for secondary analyses will be considered significant at $p<.01$.

Sensitivity analyses:

We will examine evidence of extreme outliers (+3 standard deviations from the session mean) in grams consumed for each test food, and for any outcomes identified as outliers we will examine the effect of winsorizing the outlier.

If we find evidence that meals differ in sensory ratings then we will also examine if results remain the same when sensory ratings are controlled for in analyses as a covariate.

We will also examine if results remain the same among participants who accurately identify the differences in energy density between foods vs. participants who do not. Alternatively, if only a small number of participants are unable to identify the correct order of energy density then we will examine if results remain the same when excluded.

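### Meal order is randomised with no stated balancing of the six orders, and the lunch analyses have no term for visit or for the preceding lunch

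*Combined protocol and SAP*

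**What the plan says.** The Randomization entry of the Design Plan reads "The order the conditions are presented to participants will be randomised prior to arrival". The Study flow table repeats this: "Before their first session, the order that meals are presented to participants will be randomized". Neither place mentions blocking, counterbalancing or a Latin square.

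Participants "visit the lab for three consecutive weeks" and eat each density once. The lunches are meant to raise similar expectations: "the foods provided will be variations on the same meal (loaded fries".

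The primary analysis is: "Two repeated-measures, within-subjects ANOVAs will assess lunchtime (manipulated meal) kcal and gram intake across the three conditions". Condition is its only factor. The Sensitivity analyses section covers outliers, sensory ratings and whether participants identified the densities. Nothing there concerns visit, order or the preceding lunch.

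The second hypothesis is "As energy density of the lunch meal increases from medium ED to high ED, the amount of lunch consumed (g) will decrease". The Background says of the model under test that "the calorie content signal is related to both learned and unlearned effects", and lists as a limitation of earlier work that "foods are manipulated covertly during a single session, so consumers are not able to learn about the energy content".

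**The concern.** Two separate issues follow from a three-visit crossover whose order and analysis are specified this briefly.

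The first is visit. Intake may drift over three weeks as people get used to the setting or the food. If the orders are unequally used by chance, part of that drift falls into the comparison of conditions, and a model with condition alone cannot take it out.

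The second is carry-over. Each density is served once, so no lunch can follow one of its own density. At visits 2 and 3 anything retained from the previous week comes from a different density. If a high-density lunch lowers intake of the next similar-looking lunch more than a medium one does, the medium mean is pulled down more than the high mean, and the fall predicted by the second hypothesis looks smaller than it is. That contrast bears on whether people adjust meal size at higher densities, which is the model's central claim, so it is worth knowing whether it depends on what was eaten the week before.

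**Working it through.** **Inputs from the documents.** Three conditions, three visits, six possible orders; target N = 32; pairwise effect d = 0.52; primary alpha 0.05 (Sample size and Inference criteria). **Assumptions.** Simple randomisation over the six orders, a true medium-to-high fall of 100 g, and carry-over fractions of 30% to 50%. The documents give none of these.

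**1. The plan's own figure.** A two-sided paired t-test with d = 0.52, alpha 0.05 and power 0.80 (printed as 0.8%) has power 0.79997 at N = 31 and 0.813 at N = 32. The stated 32 is reproduced.

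**2. Chance imbalance in visit position.** Over the six orders, the visit number of high minus that of medium is ±1 in four orders and ±2 in two.
- Variance per person = (4 × 1 + 2 × 4)/6 = 2.
- SD of the mean difference in 32 people = √(2/32) = 0.25 visits.
- A linear trend of T grams per week therefore adds chance error with SD 0.25T, and a 95% range of about ±0.5T.
- First-visit counts are multinomial (32; 1/3, 1/3, 1/3). The largest and smallest of the three differ by 6 or more with probability 0.46. For medium versus high alone the probability is 0.23.

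**3. Carry-over with all six orders equally used.** Let λ_L, λ_M and λ_H be the effect of last week's low, medium or high lunch on this week's grams.

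| Lunch | First visit | After low | After medium | After high |
|---|---|---|---|---|
| Medium | 1/3 | 1/3 | – | 1/3 |
| High | 1/3 | 1/3 | 1/3 | – |

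Bias in high minus medium = (λ_L + λ_M)/3 − (λ_L + λ_H)/3 = (λ_M − λ_H)/3. Balance fixes the weight at one third but does not make it zero.

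If carry-over is a fraction k of the earlier lunch's own effect, λ_M − λ_H = 100k g and the estimated fall is 100(1 − k/3) g:

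| k | Estimated fall | d = 0.52(1 − k/3) | Power at N = 32 |
|---|---|---|---|
| 0 | 100 g | 0.520 | 0.81 |
| 0.3 | 90 g | 0.468 | 0.73 |
| 0.5 | 83 g | 0.433 | 0.66 |

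**4. Price of adjusting.** In a balanced six-order design with visit in the model, adding the preceding condition multiplies the variance of high minus medium by 1.25. The SE ratio is √1.25 = 1.118, about 12% larger.

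**5. What the adjusted model could show.** Taking 100 g with d = 0.52:
- SD of differences = 100/0.52 = 192 g.
- Unadjusted SE = 192/√32 = 34 g; adjusted SE = 34 × 1.118 = 38 g.
- SE of adjusted minus unadjusted = 34 × √(1.25 − 1) = 17 g.

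The shifts of 10 to 17 g in step 3 are at most one such SE.

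**The case against.** A reader might infer that learned carry-over systematically biases the trial against the second hypothesis. The documents do not support that, for four reasons.
- Visit 1 follows no study lunch and supplies about a third of each condition's data.
- No size or sign of carry-over is given anywhere.
- The hypothesis is attributed to satiety signals, which can act within one meal and need no earlier exposure.
- The recruitment text (Appendix A) tells participants that the lunches are three variations, which weakens the idea that last week's experience is applied as if the meal were unchanged.

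Nor do the documents show that the orders are unbalanced. They state no method, and the actual list may be blocked.

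A reader might also infer that the plan would misread a null as refuting learned adjustment. The Background presents the earlier dessert study as the one on learned energy density and this one as its covert follow-up. The sample size section also expects smaller effects because the densities will be unknown to participants. No sentence claims more for a null.

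It is also fair to say that chance imbalance under randomisation is noise rather than bias, and that the proposed sensitivity model could not reliably reveal a small carry-over effect. Both points stand, and they limit the weight of the concern. They do not supply a visit term or any look at the preceding lunch. The planned split by correct identification of the densities estimates neither.

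**Conclusion.** The point holds as a gap in specification that is cheap to close. No balancing method is stated, and condition is the only factor in the lunch models.

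Under simple randomisation of 32 people, the chance difference in mean visit position has SD 0.25 visits, so a trend of T grams per week adds error with SD 0.25T; its practical size depends on a trend that the documents do not give. Under the assumption that carry-over runs in the same direction as the earlier lunch's own effect, 30% to 50% additive carry-over would reduce a 100 g fall to 90–83 g and power for d = 0.52 from 0.81 to 0.73–0.66. Carry-over of the opposite sign would enlarge the contrast instead. The primary analysis is not shown to be invalid, and the sample size target is not in question on this ground.

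**What to change.** 1. Allocate participants to the six orders in randomly permuted blocks of six, and say so under Randomization. Since 32 is not a multiple of six, the last block will be incomplete at the stated minimum.
2. Include visit as a factor with condition in the lunch gram and kcal models. This is needed even with blocking, because the completers-only rule and the exclusions can unbalance the analysed orders.
3. Pre-specify one sensitivity analysis that adds the preceding lunch's condition (none at visit 1), and show visit-1 means by condition descriptively. Visit 1 has only about 10 people per condition, so those means should not be tested.
4. Optionally, note beside the second hypothesis that a null concerns covert intake without repeated exposure to the same density.

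The cost is a new randomisation list, one more factor in the lunch models, and one extra model on data that the study already produces, provided visit order is kept in the result file. Blocking does not remove carry-over bias. Adjusting for carry-over costs about 12% in standard error and has limited ability to detect a small additive effect, so that model should inform interpretation and not replace the primary analysis.

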Upon arrival, participants will be asked to complete some questionnaires whilst their meal is being prepared. Questionnaires include:

- All three visits
 - Level of hunger/fullness
 - Cognitive task
- Final visit
 - Follow-up questionnaire (Satiety responsiveness questionnaire, compensatory health beliefs)
 - Aim guessing/ranking meals

Participants will be provided with their lunch (loaded fries). There will be a large bowl of chips (low ED; 1.17kcal/g; medium ED; 1.74kcal/g; high ED; 3.00kcal/g), and a separate large bowl of chilli at low (1.1kcal/g), medium (1.6kcal/g) or high (3.2kcal/g) ED. Participants will serve themselves from the provided bowls. The three different chilli recipes will be made in the lab using a standardised procedure. ED will be varied by altering the ingredients used, and proportions of ingredients. A review of existing energy density manipulation studies(14) found that very similar effects were identified in studies whether the nutritional composition was altered or not, so it was deemed appropriate to alter the nutritional content of the meal. Details of all food served are shown in Table 1. These recipes will be made in bulk, frozen and labelled clearly so each portion can be defrosted and prepared for each participant on the day of consumption.

Loaded fries were chosen as the test meal, as it is a food frequently served in the out-of-home food sector, and a meal which is relatively simple to manipulate in terms of energy density. The recipes

were tested several times to ensure they were equally appetising, and sent to the SGS Cambridge Analysis Lab to ensure they contained the expected energy densities.

Throughout the study, random samples of each chilli will be sent off to the SGS Cambridge Analysis Lab to test for nutritional content of each of the products. This will ensure that nutritional components remain consistent over the course of the study. We plan to do this twice over the course of data collection.

The amount of food served will fill a large serving bowl (750g of each chilli, with 500g of chips). Participants will be left alone and asked to eat as much or as little of their meal as they would like. When they have finished their meal, participants will be told to call the researcher back in to continue the study. The plate will be taken from participants and any remaining food weighed in order to calculate total grams and energy consumed. Participants will be asked to rate sensory aspects of the meal.

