After each lunch session, participants will be provided with a snack box, and told they can eat as much or as little of what is provided as they wish.

Participants will return for an evening session to eat their dinner (4.30-6.30). They will be required to bring the snack box, and any remaining snacks with them. Here, participants will once again be asked to complete hunger and fullness scales, and a cognitive task. Following this, a 3-cheese pasta ready meal (800g) with a side of mixed vegetables (225g) will be provided for participants to serve themselves. Once participants have eaten all they wish to of the pasta meal, dessert will be provided (brownie bites and flapjack bites) which once again, they can help themselves to as much or as little as they would like.

After their final study dinner, participants will be given a follow-up questionnaire to assess compensatory health beliefs and satiety responsiveness. They will also be asked to guess the aim of the study and rank the foods they have eaten for each lunch session in terms of healthiness. Following this they will be fully debriefed.

Table 1: All test foods

	Low ED			Medium ED			High ED		
	g	kcal	£	g	kcal	£	g	kcal	£
LUNCH									
Potatoes	500	585	£1.27	500	870	£0.97	500	1500	£2.16
Chilli	750	885	£3.17	750	1275	£3.14	750	2430	£3.92
Water	500	0	£0.00	500	0	£0.00	500	0	£0.00
DINNER									
Ready meal	800	1164	£3.50	800	1164	£3.50	800	1164	£3.50
Mixed vegetables	225	84	£1.50	225	84	£1.50	225	84	£1.50
Water	500	0	£0.00	500	0	£0.00	500	0	£0.00
DESSERT									
Brownie bites	220	860	£2.25	220	860	£2.25	220	860	£2.25
Flapjack bites	280	1260	£2.25	280	1260	£2.25	280	1260	£2.25
Water	500	0	£0.00	500	0	£0.00	500	0	£0.00
SNACKBOX									
Apple	268	142.04	£0.80	268	142.04	£0.80	268	142.04	£0.80
Cereal bar	60	232.8	£0.67	60	232.8	£0.67	60	232.8	£0.67
Crisps	50	270	£0.18	50	270	£0.18	50	270	£0.18
Carrot batons	100	43	£0.58	100	43	£0.58	100	43	£0.58

Biscuits	22	104.72	£0.17	22	104.72	£0.17	22	104.72	£0.17
Dried fruit and nut mix	25	133	£0.55	25	133	£0.55	25	133	£0.55
Chilli									
Mince (5%/15%/20%)	250		£1.43	313		£1.82	769		£2.75
Onion	75		£0.04	68		£0.03	12		£0.01
Carrot	100		£0.05	52		£0.03	6		£0.01
Mushroom	100		£0.30	52		£0.16	6		£0.02
Tomato	100		£0.27	52		£0.14	6		£0.02

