DINNER	
After completing hunger and fullness ratings and a cognitive task again, participants will be provided with a glass of water and a ready-meal for dinner, which they can serve themselves.
 
After dinner, participants will be provided with a dessert to have as much or as little of as they like.
	
After completing hunger and fullness ratings and a cognitive task again, participants will be provided with a glass of water and a ready-meal for dinner, which they can serve themselves.
 
After dinner, participants will be provided with a dessert to have as much or as little of as they like.
	
After completing hunger and fullness ratings and a cognitive task again, participants will be provided with a glass of water and a ready-meal for dinner, which they can serve themselves.
 
After dinner, participants will be provided with a dessert to have as much or as little of as they like.

POST-MEAL	Participants will complete hunger and fullness ratings and a cognitive task again.	Participants will complete hunger and fullness ratings and a cognitive task again.	Participants will complete hunger and fullness ratings and a cognitive task again. Participants will complete measures of satiety responsiveness (Appendix F) and compensatory health beliefs (Appendix G).
DEBRIEFING			Aim guessing in an open-ended response format will be provided to participants (Appendix H). Following this, participants will be asked to rank the meals from the three weeks in order of energy density. Participants will be debriefed on study aims (Appendix H).
DATA MANAGEMENT	
The result files will contain:
 
 ○ Participant unique ID (randomly generated) ○ Demographic and questionnaire data ○ Amount of each lunch meal consumed (g) ○ Energy consumed for each lunch (kcal) ○ Snacks consumed ○ Amount of dinner and dessert consumed (g) ○ Energy consumed for dinner and dessert (kcal) 		

Analysis Plan

Participant characteristics:

Only participants who have completed the entire study (all three visits) will be included in analysis. We will report analyses with any participants who guess the aims of the study included and excluded.

If any participants do not follow study instructions (e.g. do not consumer any or only a very small amount of any of the food (<50kcal) then they will be removed from primary analyses.

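### The Procedure contradicts itself on when the final-visit questionnaires, aim guess and meal ranking are given: once before the third lunch, once after the last dinner

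*Combined protocol and SAP*

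**What the plan says.** The documents time the final-visit measures in four places.

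- **Procedure, arrival step.** "Upon arrival, participants will be asked to complete some questionnaires whilst their meal is being prepared". The list that follows has one group for all three visits (hunger/fullness and the cognitive task) and one for the final visit: "Follow-up questionnaire (Satiety responsiveness questionnaire, compensatory health beliefs" and "Aim guessing/ranking meals". The next step is "Participants will be provided with their lunch (loaded fries".
- **Procedure, evening session.** "After their final study dinner, participants will be given a follow-up questionnaire to assess compensatory health beliefs and satiety responsiveness". It continues: "They will also be asked to guess the aim of the study and rank the foods they have eaten for each lunch session". Debriefing comes after that.
- **Variables, Aim guessing (Appendix H).** "At the end of their final visit, participants will be asked what they believe the aims of the study to be". The ranking follows the aim question.
- **Study flow table.** The visit 3 baseline row, before lunch, holds only hunger/fullness and the cognitive task. The visit 3 row after dinner says "Participants will complete measures of satiety responsiveness (Appendix F) and compensatory health beliefs (Appendix G". The debriefing row holds the aim question and then the ranking.

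Two analyses depend on these measures. The Analysis Plan reports results with aim-guessers included and excluded. The Sensitivity analyses section compares participants who do and do not identify the energy-density differences correctly.

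**The concern.** The manipulation is meant to be covert, and recruitment uses a cognitive-function cover story to limit aim guessing. Appendix G items 5 to 8 deal openly with trading a small or large meal, or a snack, against what is eaten at another time. Appendix H asks for the three lunches to be ordered by healthiness. Read just before the third self-served lunch, this material could change the primary outcome at that visit, and also the snack and dinner intakes that make up the secondary outcomes.

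The checks on blinding would suffer too. Awareness coded before the third lunch says nothing about awareness during or after it, and would miss awareness created by the questions themselves. A ranking made before the third lunch cannot reflect that meal.

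A smaller issue remains under the end-of-visit timing. Both the evening part of the Procedure and the Study flow table put the compensatory-beliefs form before the aim question, so the form can suggest the answer that is then coded as awareness.

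**Working it through.** No planned figure is in dispute. The check is a comparison of texts, plus a count of the observations exposed.

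**1. Timing, item by item**

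| Measure | Procedure, arrival step | Procedure, evening session | Aim guessing section | Study flow, visit 3 |
|---|---|---|---|---|
| Satiety responsiveness, compensatory beliefs | before lunch | after dinner | not covered | after dinner |
| Aim question | before lunch | after dinner | end of visit | debriefing |
| Meal ranking | before lunch | after dinner, of foods eaten | after the aim question | debriefing, after the aim question |

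Every measure has at least two statements against the arrival step, and one of them is always in the Procedure itself. The visit 3 baseline row of the Study flow table also leaves these measures out of the pre-lunch set.

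**2. Is the arrival list just a general inventory of questionnaires?** Two features count against that. It omits the sensory ratings, which the same part of the Procedure places after the meal. Its items for all three visits are exactly those in the pre-lunch rows of the Study flow table for visits 2 and 3. It therefore reads as an on-arrival list, and staff preparing lunch could use it as one.

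**3. Observations exposed if the arrival list were followed**

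- Inputs: planned minimum of 32 participants (Sample size section); three lunches each (Study design).
- Lunches in total: 32 × 3 = 96. Lunches at visit 3: 32. Share: 32/96 = 1/3.
- The same share applies to later intake and daily intake.
- Lunches eaten when the ranking is made: 2 of 3.

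**4. What the analysis would do with a visit 3 shift.** The planned repeated-measures ANOVAs name no visit or order term, so a shift would not be adjusted for. Write dH and dM for the visit 3 shifts in the high and medium conditions. With each condition falling at visit 3 for one third of participants, the high-minus-medium mean difference moves by (dH − dM)/3. A shift common to all conditions cancels; one that differs by condition leaves a third of the difference. The documents give no value for dH or dM.

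**5. Which items could plausibly prime intake**

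- Appendix F: general self-description of fullness; little.
- Appendix G items 1 to 4: exercise; little.
- Appendix G items 5 to 8: portions, snacks and later eating; plausible.
- Appendix H aim question: open-ended, discloses nothing of the hypothesis.
- Appendix H ranking: draws attention to healthiness; plausible.

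**6. Order at the end of the visit.** The current sequence is Appendix F and G, then the aim question, then the ranking. The coding rule counts as aware anyone who links the healthiness or energy content of the meal to how much was eaten at lunch or dinner. Items 5 to 8 supply much of that idea just before the question is asked.

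**The case against.** The best defence is that this is a drafting slip. Each specific timing statement outside the arrival list points to the end of the visit, and the evening part of the Procedure is explicit. The arrival list also cannot be carried out in full as written, since it would require ranking a meal not yet served. That argument stands as to intent: the documents do not show that the sponsor chose pre-lunch administration. It does not remove the conflict, because a registered plan should give one time point and the list reads as an instruction for arrival.

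A reader might infer that visit 3 intake will be primed. The documents do not support that. The harm arises only if staff follow the arrival list over the other statements.

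A reader might also infer that all these forms reveal the hypothesis. Only Appendix G items 5 to 8 and the healthiness ranking plausibly do so. Items 5 to 7 concern compensation at another eating occasion, which is closer to the secondary question than to adjustment within lunch.

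Finally, a reader might attach a size to the problem through order imbalance. If order were assigned by simple randomisation, the difference between the numbers receiving the high and medium lunches at visit 3 would have an SD of √(32 × 2/3) = 4.6 participants; with balanced orders it would be close to zero. The documents say only that order is randomised, and this figure measures imbalance in counts, not any effect on intake.

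**Conclusion.** The Procedure contradicts itself, and its arrival step also conflicts with the Study flow table and the Aim guessing section. End of visit is the apparent intention. If the arrival list were followed, one third of lunches (32 of 96 at the planned minimum) and the same share of later and daily intakes would come after material that could prime eating. The ranking would include an uneaten meal, and aim awareness would be recorded too early for the analysis that uses it. These consequences are conditional, and the size of any priming effect cannot be derived from the documents.

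Separately, and whichever time point is kept, asking about compensation beliefs before the study aim can inflate the count of aware participants and so distort the comparison with aim-guessers included and excluded. The size of that inflation cannot be derived either.

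**What to change.** 1. In the Procedure, delete the final-visit bullets from the on-arrival list, leaving hunger/fullness and the cognitive task before lunch at all three visits.
2. State one time point for the Appendix F, G and H measures: after the visit 3 dinner, dessert and post-meal ratings. This agrees with the evening part of the Procedure, the Aim guessing section and the Study flow table.
3. In the evening part of the Procedure and in the Study flow table, move the open-ended aim question ahead of the Appendix G items, keeping it ahead of the meal ranking. This changes the stated order and is not needed to resolve the timing conflict; it protects the awareness coding.

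The cost is a wording edit and a reordering of existing forms, with no added visits, staff or measures. It should be done before the first participant reaches visit 3, because intake measured after such prompts could not be recovered by analysis.
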